Dose escalation will start with dose tier 1 and proceed to dose tier 2 in the absence of RLTs. Otherwise the dose will be de-escalated to tier -1. The escalation/de-escalation schema uses the following table. Under this schema, more than one patient can be enrolled at the same time; however, *within Phase 1, CKM cannot be started on the next patient until the previous patient completes the cycle of CKM and an additional one week of observation for potential RLTs (total of two week difference between the consecutive patients). Also, CKM cannot be started on the next dose until 2 patients on the lower dose complete the CKM regimen and additional one week of observation for potential RLTs.* Similar rule will be applied during the escalation between different tiers and for the patients within the same dose tier, in order to allow time to evaluate any potential toxicities.

The establishment of the RP2D will be based on an adaptive design for which the next dose will be set according the following rules:

Dose Escalation/De-escalation Rules

Observed Number of RLTs on a Dose Tier	Decision Rule for the Next Subject
There is at least 1 RLT among the last 2 subjects treated on this dose tier and the proportion of DLTs on this dose tier is > 0.30	Assign to next lower dose
There are no RLTs among the last 2 subjects treated on this dose tier and the proportion of RLTs among all subjects on this dose tier is ≤ 0.30	Assign to next higher dose
Neither of the above is satisfied	Assign to the same dose

If no RLTs are observed among the first 3 dose tiers, four additional patients will be added to tier 3 for a total of 6 on tier 3. If, after treating 10 patients without RLT (2 + 2 + 6), dose tier 3 will be declared the RP2D. If an RLT is observed at any dose tier the adaptive up-and-down design will commence until 15 patients are observed after which the Phase 2 starting dose will be estimated by isotonic regression.

Regimen limiting toxicities (RLTs) are defined as the following toxicities:

Vaccine possibly, probably or definitely related RLTs

- Grade 2 or more bronchospasm or generalized urticaria (hypersensitivity)
- Grade 2 or more allergic reaction
- Grade 3 injection site reaction due to vaccine
- > Grade 3 toxicity of any kind related to the DC vaccine

CKM possibly, probably or definitely related RLTs

- Grade ≥ 3 leukopenia or neutropenia persisting ≥ 4 days (96 hours) after treatment

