- Greater than or equal to grade 3 non-hematologic adverse events, except for the following grade 3 toxicities unless they last greater than one week:
 - Flu-like symptoms/constitutional symptoms (i.e., fever, chills, arthralgias, myalgias)
 - Depression, anxiety, restlessness, or insomnia
 - Manageable GI symptoms (i.e., nausea, diarrhea)

The observation period for each patient in the Phase 1 portion of this study will be up to 5 weeks (i.e. up to and including the Friday 1 week after the end of the chemokine modulating regimen).

Note: The last 2 patients in the Phase 1 cohort that determines the RP2D will continue on to the Phase 2 part of the trial and will receive the 2nd and 3rd booster/CKM cycles and follow-up per the Phase 2 portion of this protocol. All patients in the dose finding cohort will be followed for primary efficacy endpoints as well as have blood and serum drawn for corollary studies.

Patients in the Phase 1 (safety) cohort will receive their study treatment and will be monitored for RLTs according to the following timeline:

Eligibility	ECOG performance status, blood work CRS + HIPEC
Screening	History and physical exam, ECOG performance status, blood work, and evaluation of tumor material
Post-surgery (after the discharge from the hospital)	Leukapheresis
Week 1* (upon recovery from surgery; at least 4 weeks after surgery)	Priming Vaccine dose; no chemokine modulation Monday: α DC1 vaccine Oral celecoxib, 200 mg, twice daily on the day of vaccination Tues – Sun: oral celecoxib 200mg, once daily
Weeks 2-3	Rest – continue oral celecoxib, 200 mg, once daily
Week 4	Cycle 1 (“booster cycle”) Monday: α DC1 vaccine Tues – Fri: Systemic Chemokine Modulation Regimen. Oral celecoxib, 200 mg, twice daily on the days of vaccination and CKM. Celecoxib will be discontinued after CKM on Friday. Rintatolimod is only administered on Wednesday and Friday.
Off study treatment	Follow-up for Time-to-Progression/occurrence (TTP)

CRS: Cytoreductive surgery; HIPEC: Hyperthermic intraperitoneal chemoperfusion; TTP: Time-to-progression

*Adjuvant immunotherapy may be delayed until full recovery at the discretion of the investigator/sub-investigator. The beginning of immunotherapy will be considered week 1 of the experimental treatment and the timing of all subsequent elements of treatment will be based upon the first vaccine.

5.2 Phase 2: Efficacy assessment of α DC1 vaccine followed by the chemokine-modulatory regimen (CKM)

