7.1.3 Interferon- α 2b

IFN α may cause fever, chills and flu-like symptoms; loss of appetite; nausea; vomiting, diarrhea and abdominal pain; fatigue; lowered white blood count may increase risk of infection; lowered

platelets may lead to an increase in bruising or bleeding; hair loss. Other risks which may be common in cases of prolonged administration include drowsiness; temporary confusion; anxiety, amnesia, irritability, confusion, delusions and depression which can be severe; numbness and/or tingling in the hands and/or feet, skin rashes and inflammation of the pancreas. Inflammation of the pancreas is swelling or irritation of the pancreas which may result in tenderness or pain in the stomach and/or back. When the pancreas is inflamed, the body is not able to absorb all the nutrients it needs.

For more risk information reference the Investigator's Brochure or package insert.

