Rintatolimod has been dosed in combination with alpha interferon in investigator initiated studies under investigator IND applications during the period between December 1985 and April 1994. A total of 24 patients received combination treatments. Clinical conditions included renal cell carcinoma, chronic myelogenous leukemia, melanoma, and ovarian cancer. Rintatolimod was given as an IV infusion at a dose of 300 mg BIW. The starting dose was sometimes as low as 1-10 mg. The interferons were administered at a dose of 3 million Units daily, with some doses of 0.75 mU at the low side and up to 6 mU at the higher side.

The therapy with rintatolimod in combination with alpha interferon was generally well tolerated without evidence of dose-limiting or cumulative toxicities. The most frequent adverse reactions were considered minor in severity and duration. Most of them were flu-like symptoms such as chills, cold feeling, fatigue, decreased appetite, fever, muscular aches. Also shortness of breath has been seen as well as hypotension, nausea, anemia, dyspnea, numbness, itching and blurred vision. These adverse events were judged possibly related to the condition of the patients, but also possibly related to the administration of rintatolimod or interferon. In some cases worsening of the patient's condition has been seen due to tumor progression, but in general favorable clinical patterns were observed in these patients with advanced disease. Such combinations were not intended to be immune modulating and were evaluated in the context of clinical cancer care.

For more risk information reference the Investigator's Brochure.

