6. Peripheral blood for potential correlative studies will be collected at the following time points: once during the pre-screening, within 60 minutes before the vaccinations of the priming cycle, and booster cycles 1 and 2; and within 60 minutes after completing booster cycle 2 on Friday. Peripheral blood for potential correlative studies may additionally be drawn within 60 minutes before the vaccination of booster cycle 3 on Monday and within 60 minutes after completing booster cycles 1 and 3 on Friday.
7. Performed within 2 weeks prior to the priming dose of vaccine and 5 business days prior to cycles 1, 2 and 3 vaccines.
8. CT or MRI imaging should be performed prior to cycle 1 if the recovery period from surgery is greater than 6 weeks.
9. At the discretion of the treating physician, the tests/procedures due to be performed at the Off Study Treatment visit may be performed on the last day of the CKM treatment for scheduling purposes.
10. Performed as routine pre-operative evaluation.
11. AEs /conmeds should be collected up to 5 days after treatment, unless considered clinically significant or serious in nature in which case they will be followed until resolution or Grade 1.

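### The Phase 1 toxicity definition for the chemokine regimen has no platelet or hemoglobin criterion, and no blood count is scheduled in the window where it is judged

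*Combined protocol and SAP*

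**What the plan says.** Section 5.1 states that RLTs are the toxicities it lists, with no catch-all. Under CKM, events at least possibly related count if they are grade 3 or higher "leukopenia or neutropenia persisting" at least 4 days (96 hours) after treatment, or "Greater than or equal to grade 3 non-hematologic adverse events". The second item excuses some grade 3 flu-like, mood or sleep, and manageable gastrointestinal symptoms unless they last more than a week. Under the vaccine, the widest item is anything more severe than "Grade 3 toxicity of any kind related to the DC vaccine", if at least possibly vaccine-related.

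The RLT count drives the escalation table. It also drives the rule that, after 10 patients (2 + 2 + 6) without an RLT, "dose tier 3 will be declared the RP2D", and otherwise the isotonic estimate after 15 patients. Section 6.1 (removal from treatment) and section 13.4 (Bayesian suspension rule) use the same term, and no second definition is given. The Phase 1 observation window runs "up to and including the Friday 1 week after the end of the chemokine modulating regimen".

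On the drugs, section 7.1.3 says that with interferon lowered "platelets may lead to an increase in bruising or bleeding". Section 7.1.4 lists anemia among events with rintatolimod plus interferon, "judged possibly related to the condition of the patients, but also possibly related to the administration of rintatolimod or interferon". Neither gives a grade or a rate.

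In the section 10 calendar, note 7 places blood counts before the priming dose and within "5 business days prior to cycles 1, 2 and 3 vaccines". The off-treatment column has no blood count. The optional Friday draw after cycle 1 (note 6) is for correlative studies.

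**The concern.** One CKM item covers white cells only and the other excludes hematology, so platelets and hemoglobin fall between them. This looks like an oversight: section 5.1 names the grade 3 toxicities it is willing to tolerate, and cytopenias are not among them. Interferon is the drug escalated from 5 to 20 MU/m², and the protocol itself links it to lowered platelets.

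The protocol also treats the same event in two ways. In Phase 2, section 6.2.2 requires a hold and a 33% cut in interferon and rintatolimod for any grade 3 CKM toxicity. In Phase 1, a grade 3 platelet event does not count against the dose being chosen. If such events were common, interferon would be escalated, and tier 3 could become the RP2D, with those events scored as zero.

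**Working it through.** **What counts as an RLT for a CKM-related blood event (section 5.1)**

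| Event | CKM list | Vaccine list |
|---|---|---|
| Grade 3+ leukopenia or neutropenia, 4 days or more | counts | grade 4+ if possibly vaccine-related |
| Grade 3 thrombocytopenia or anemia | no | no |
| Grade 4 thrombocytopenia or anemia | no | only if possibly vaccine-related |
| Grade 3+ bleeding | counts (non-hematologic) | grade 4+ if possibly vaccine-related |

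The booster is given the day before CKM starts, so many grade 4 events could be called possibly vaccine-related. What remains uncounted is grade 3, and grade 4 attributed to CKM alone.

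**Escalation table, one constructed case.** Suppose both tier 2 patients have grade 3 thrombocytopenia for 5 days and the counts are known. As written, RLTs are 0/2 and the next dose is higher (interferon 10 to 20 MU/m²). With persistent grade 3 thrombocytopenia counted, RLTs are 2/2 = 1.00 > 0.30 and the next dose is lower (5 MU/m²).

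**RP2D.** Let q be an assumed rate of newly counted events at tier 3, with no other RLTs. As written, tier 3 is declared with probability 1 for any q. With the events counted, an exact recursion over the section 5.1 rules (start at tier 1; table applied after each patient; stop at 10 if no RLT; otherwise 15 patients and a pooled-adjacent-violators fit) gives the chance that tier 3 is still chosen. Section 5.1 does not say how the isotonic fit selects a dose, so two readings are shown: the highest tier with an estimate of 0.30 or less, and the tier nearest 0.30. In the graded case the rate is q/2 at tier 2 and q/4 at tiers 1 and −1.

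| q | Tier 3 only: highest / nearest | Graded: highest / nearest |
|---|---|---|
| 5% | 99% / 100% | 99% / 100% |
| 10% | 96% / 100% | 93% / 98% |
| 20% | 78% / 98% | 70% / 86% |
| 30% | 53% / 93% | 42% / 66% |
| 40% | 30% / 82% | 21% / 43% |

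**Section 13.4, plan's figures first.** The posterior is 1 − BetaCDF(0.30; 1.93 + r, 4.74 + n − r). For r = 5, n = 10 this is 0.831 (4 RLTs give 0.667). For r = 56, n = 168 it is 0.812 (55 give 0.765). All 22 printed rows reproduce, so the arithmetic is sound and only the event definition is in question.

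Applying the boundary after every patient to 168, with independent assumed rates r (already counted) and h (newly counted), the full rate is 1 − (1 − r)(1 − h):

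- r = 20%, h = 0: suspension 11%.
- r = 20%, h = 10%: 1 − 0.8 × 0.9 = 28%, suspension 44%.
- r = 20%, h = 15%: 1 − 0.8 × 0.85 = 32%, suspension 73%.
- r = 20%, h = 20%: 1 − 0.8 × 0.8 = 36%, suspension 93%.

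The last three assume that every event is detected. If only half of the h = 20% events are detected, the rate seen is 28% and suspension is 44%.

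**Calendar.** Phase 1 patients have one CKM cycle. Their last scheduled count precedes the cycle 1 vaccine. The off-treatment visit, 1–2 weeks after the last treatment day (section 5.8), has none. The two patients who continue into Phase 2 have their next count before booster cycle 2, which is due 4–12 weeks after cycle 1 and so falls outside the window.

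**The case against.** **RLT thresholds are a clinical choice.** This stands in part. Any sensible added criterion will still leave something uncounted, such as grade 3 anemia or brief grade 3 thrombocytopenia without bleeding. But the protocol does not state the omission as a choice.

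**The rate may be low.** Section 2.6.3 reports a similar regimen with daily rintatolimod reaching 20 MU/m² without regimen limiting toxicities, and section 7.1.4 reports no dose-limiting hematologic toxicity for rintatolimod. This stands as a reason to expect a small effect. It does not show that cytopenias were absent, because the earlier trial's RLT definition is not given.

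**Patients are protected in other ways.** This is correct. Section 6.2.2 holds and reduces CKM in Phase 2, section 5.7 stops treatment for unacceptable agent-specific events, Phase 1 patients are staggered by two weeks, and the monitoring bodies in section 12.1 can suspend accrual. A reader might infer that platelet toxicity goes unmanaged; the documents do not support that. None of these provisions, however, changes the RLT count.

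**Section 6.1 hardly matters.** Agreed. After a single CKM cycle there is almost no Phase 1 treatment left to remove a patient from.

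**The dose-selection effect is confounded.** At q = 30% in the tier-3-only case the answer is 53% or 93%, depending on a selection rule that section 5.1 leaves open. A reader might also take the chance of no RLT in 10 patients, 0.7^10 = 0.03 at q = 30%, as the chance that tier 3 survives. It is not: after an RLT the design continues to 15 patients and can still select tier 3.

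**Conclusion.** The definitional gap and the calendar gap are both plain in the text. The calendar gap is the more concrete of the two, because it also affects the white-cell criterion already in the protocol, and without a post-CKM count a platelet criterion would rarely change a Phase 1 decision.

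The consequence is of unknown size, since every rate above is assumed. At 10% or less at tier 3 the effect is small (93–100% still choose tier 3), and choosing tier 3 there is within the protocol's own tolerance. It becomes material as the rate approaches or passes 30%.

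The 73% and 93% suspension figures are ceilings. They need every Phase 2 event to be seen, and the scheduled pre-cycle counts would miss short-lived cytopenias. Nor do the documents support reading this as showing that the RP2D is wrong or that patients are unsafe. It is a cheap improvement worth making.

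**What to change.** 1. Add a blood count with platelets and differential in the week after the Phase 1 CKM cycle, repeated if any count is grade 3 or higher so that 4-day persistence can be judged.
2. Add CKM-related criteria to section 5.1, for example grade 4 thrombocytopenia, grade 3 thrombocytopenia with bleeding or lasting at least 4 days, and grade 4 anemia. Clinicians should confirm the thresholds. If grade 3 anemia stays uncounted, say so as a choice.
3. State in section 13.4 that it uses the same list, and that Phase 2 detection rests on pre-cycle and clinically indicated counts, so brief cytopenias between cycles or after cycle 3 may be missed.

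The cost is a few lines of text, one routine draw per Phase 1 patient (a repeat if grade 3 or higher), and possibly slower escalation. It also needs IRB approval and an IND amendment, since section 12.4 names an added safety test as requiring one. Section 13.4 would suspend for review somewhat more often, even below the 30% target: from 11% to at most 44% when 10% newly counted events join 20% others.

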Study treatment will consist of one priming dose of DC vaccination followed by 3 booster cycles of DC vaccine + chemokine modulation regimen (CKM), cycles 1-3. The booster vaccine is administered on Monday followed by 4 days of the CKM regimen (Tuesday – Friday).

Timing of the experimental treatment:

- Priming cycle: 6 to 16 weeks after surgery (target: 8 weeks)
- Booster cycle 1: 4 to 12 weeks after priming cycle (target: 4 weeks)
- Booster cycle 2: 4 to 12 weeks after booster cycle 1 (target: 4 weeks)
- Booster cycle 3: 4 to 12 weeks after booster cycle 2 (target: 4 weeks)

It is expected that a significant proportion of the patients will undergo adjuvant clinically indicated chemotherapy. Adjuvant chemotherapy can be administered between the courses of immunotherapy, but no sooner than 5 days after finishing any cycle of immunotherapy. The following cycle of immunotherapy will start no sooner than 5 days after the last day of a chemotherapy cycle and after recovery from acute side effect of chemotherapy.

Patients who (for clinical or logistic reasons) will not be able to take any cycle of immunotherapy within the above-indicated windows, can still receive the remaining courses of immunotherapy at later time points, but will not be included in the analysis of the primary efficacy endpoint, although they can be analyzed in an exploratory manner.

Similarly, patients who (for clinical or logistic reasons) will not be able to receive the priming dose of vaccine within 3 months after surgery, can still receive immunotherapy at later time points, but will not be included in the analysis of the primary efficacy endpoint, although they can be analyzed in an exploratory manner.

In the efficacy phase, patients will receive a priming dose of the α DC1 vaccine followed by 3 courses of the α DC1 booster vaccine combined with CKM regimen as illustrated in the following table:

Eligibility	Informed Consent CRS + HIPEC
Screening	History and physical exam, ECOG performance status, blood work, evaluation of tumor material
Post-surgery (within the first 8 weeks following surgery)	Leukapheresis
Week 1* (upon recovery from surgery; no sooner than 6 weeks post-surgery)	Priming Vaccine dose; no chemokine modulation) One day: α DC1 vaccine Oral celecoxib, 200 mg, before and after treatment on the day of vaccination
Weeks 2-3	Rest
Week 4 (target)*	Booster Cycle 1 Monday: α DC1 vaccine

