5.5 Continuation of Booster Vaccines Administration

At the discretion of the treating physician, any patient who completes study treatment or is removed for reasons other than vaccine related AE/SAEs may continue to receive available vaccine. These vaccines may be administered 4-12 weeks apart. Subjects removed will continue to be evaluated for safety, but not be included in the analysis of formal efficacy objectives but may be evaluated in an exploratory manner. These subjects will be evaluated/followed based upon the conventional care evaluations outlined in the study calendar on days of vaccination (i.e., PE, vitals, AE evaluation).

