5.7 Duration of Study Treatment

In the absence of treatment delays due to adverse event(s), treatment may continue until one of the following criteria applies:

- Disease progression (excluding disease progression during the time between surgery and the CKM regimen, these patients will be allow to continue with study treatment). See also Section 5.5.
- Patient withdraws consent but allows continued follow-up for survival
- Patient non-compliance
- Unacceptable agent specific adverse event(s).
- General or specific changes in the patient's condition render the patient unacceptable for further treatment in the judgment of the investigator/sub-investigator.
- Pregnancy in patient

The reason and date a patient was removed from study treatment must be documented.

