11. MEASUREMENT OF EFFECT

All Patients will undergo CT or MR prior to returning for cycle 2 of the investigational treatment (approximately week 6 or 7), at the time of the off treatment visit at MD discretion, and subsequently based upon the timing the regular care for their cancer. Response or progression will primarily be evaluated by CT or MR imaging of tumor nodules using RECIST criteria v1.1, however tumor measurements are not required as patients must be completely surgically resected to be eligible.

11.1 Disease Parameters (May be used as a guideline for scan review prior to Cycle 2)

Measurable disease: Measurable lesions are defined as those that can be accurately measured in at least one dimension (longest diameter to be recorded) as ≥ 10 mm with CT or MR imaging (CT/MR slice thickness no greater than 5 mm). Malignant lymph nodes may be considered measurable disease if they are ≥ 15 mm in short axis as measured by CT or MR imaging with no greater than 5 mm slice thickness.

Non-measurable disease: All other lesions (longest diameter < 10 mm with CT or MR scan) are considered non-measurable disease. Bone lesions, ascites, leptomeningeal disease, pleural/pericardial effusions, lymphangitis cutis/pulmonis, inflammatory breast disease are all non-measurable.

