11.3 Duration of Response

Time-to-Progression (TTP): Time-to-Progression is measured from the start of treatment until the criteria for progression are met

Duration of overall response: The duration of overall response is measured from the time of surgical resection until the first date that progressive disease is objectively documented (taking as reference for progressive disease the smallest measurements recorded since the treatment started).

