13.3 Data Analysis

At the completion of follow-up in evaluable patients, we will estimate progression-free survival by the Kaplan-Meier method with Greenwood 90% confidence intervals. We will conduct a formal test of the hypothesis that progression-free survival is improved with the experimental therapy. This test will be a one sided exponential test at $\alpha = .10$ that the median progression-free survival is better than 25% compared to historical controls. If this test is significant we will conclude that the progression-free survival is improved compared to the historical control. Descriptive summaries will be prepared of all adverse events by grade, frequency and attribution. An assessment of the association between immune parameters and survival will be conducted. The panel of immune parameters will be tested for association with progression-free and overall survival with Cox proportional hazards regression.

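### Membership of the primary TTP analysis depends on booster timing after the TTP clock has started, the evaluable set is undefined, and no all-treated analysis is planned

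*Combined protocol and SAP*

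**What the plan says.** - **Clock.** Section 11.3: "Time-to-Progression is measured from the start of treatment until the criteria for progression are met". Section 5 counts week 1 from the start of postoperative immunotherapy, so I take the priming dose as time zero.
- **Exclusion.** Section 5.2 covers patients who, for clinical or logistical reasons, "will not be able to take any cycle of immunotherapy within the above-indicated windows". They may be treated later, "but will not be included in the analysis of the primary efficacy endpoint, although they can be analyzed in an exploratory manner".
- **Analysis set.** Section 13.3 opens with "At the completion of follow-up in evaluable patients". The term is not defined anywhere.
- **Replacement.** Section 3 enrols a new patient when a recruited patient is excluded or resigns.
- **Removed patients.** Section 5.5: "Subjects removed will continue to be evaluated for safety, but not be included in the analysis of formal efficacy objectives". It continues: "These subjects will be evaluated/followed based upon the conventional care evaluations outlined in the study calendar on days of vaccination". Section 5.7 makes progression a reason to stop treatment, except between surgery and CKM, where "these patients will be allow to continue with study treatment). See also Section 5.5".
- **Follow-up.** The section 5.2 table and section 5.9 keep following patients for progression after treatment ends.
- **Scans.** Section 11: "All Patients will undergo CT or MR prior to returning for cycle 2 of the investigational treatment" (about week 6 or 7). The off-treatment scan is at the physician's discretion.

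**The concern.** The booster windows close well after time zero. A patient's place in the primary analysis therefore depends on what happens while TTP is already running. Clinical reasons for delay, such as toxicity or recovery from adjuvant chemotherapy, may be related to prognosis. There is no concurrent control to share the exclusions: the comparison is with fixed historical medians (section 13.2). If delayed patients do worse than the rest, leaving them out flatters the regimen; if they do better, it penalises it.

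The exploratory analysis is optional and unspecified, so it does not repair the formal test. With *evaluable* undefined, two analysts could form different primary sets from the same data.

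**Working it through.** **1. The plan's own sample size.** Inputs from sections 13.2 and 13.3: historical medians 20, 20 and 12 months (mesothelioma, appendiceal, colorectal), ratio 1.25, one-sided alpha 0.10, power 90%, 36 months' accrual plus 18 months' follow-up, 168 patients. I use the yearly case numbers 15:40:60 as the histology mix.

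- Events needed = (1.2816 + 1.2816)² / (ln 1.25)² = 131.9.
- P(event) = 1 − [exp(−18λ) − exp(−54λ)] / (36λ), with λ = ln 2 / median. This gives 0.694 at 20 months and 0.851 at 12 months.
- Weighted: (55 × 0.694 + 60 × 0.851) / 115 = 0.776.
- N = 131.9 / 0.776 = 170. Power at 168 is 89.7%.

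So 168 reproduces with a null of no improvement (ratio 1.0). It contains no allowance for exclusions.

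**2. When membership is settled.** Each booster follows the previous cycle by 4 to 12 weeks, so booster 3 falls 12 to 36 weeks after priming. Section 6 allows a delay of up to 8 weeks. Added to the 4-week target this is 4 + 8 = 12 weeks, the upper end of the window.

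**3. Simulation set-up.** 60,000 trials per scenario, exponential TTP from priming, uniform accrual, analysis at month 54. E is summed exposure times the histology-specific null hazard and d is the number of events. Reject if ln(E/d) × √d > 1.2816. With no true effect and no exclusions the rejection rate is 0.09 to 0.10.

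**4. Booster-window exclusion (section 5.2).** Assumption: a share q of patients has hazard r times that of the rest, scaled so that the median of all treated patients equals the historical one. These patients are then excluded and replaced to 168.

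| q | r | Rate, excluded | Rate, all kept |
|---|---|---|---|
| 10% | 0.8 | 0.06 | 0.10 |
| 10% | 1.0 | 0.09 | 0.09 |
| 10% | 1.25 | 0.15 | 0.10 |
| 10% | 1.5 | 0.20 | 0.10 |
| 10% | 2.0 | 0.31 | 0.12 |
| 20% | 1.5 | 0.36 | 0.11 |
| 20% | 2.0 | 0.63 | 0.14–0.15 |

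The last column rises with r because a mixture is not exponential. That part of the inflation is not due to exclusion.

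Hand check for q = 10%, r = 2.0: solve 0.9x + 0.1x² = 0.5, so x = 0.525. The retained patients' median ratio is ln 2 / (−ln 0.525) = 1.076. With about 127 events, Φ(√127 × ln 1.076 − 1.2816) = 0.32, in line with the simulated 0.31.

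**5. Section 5.5, if progressors are dropped.** Week 1 is the priming week, so the one required scan at study weeks 6–7 falls 5–6 weeks after priming. Dropped and replaced, no true effect:

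| Progressions dropped | Share of patients if all dropped | All | Half | A quarter |
|---|---|---|---|---|
| Booster 1 at 4 weeks, to the scan | 1.0–2.0% | 0.12–0.15 | 0.11–0.12 | 0.10–0.11 |
| Booster 1 at the table's Week 4, to the scan | 2.1–3.1% | 0.15–0.18 | 0.12–0.13 | 0.11 |
| Weeks 4–12 after priming | 7.8% | 0.42 | 0.22 | 0.15 |

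Replacement hardly matters: without it the last row is 0.40, 0.21 and 0.15.

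**6. The other reading of the null.** Section 13.3 can also be read as testing for an improvement larger than 25%. With 1.25 as the null, every rate above is below 0.02.

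**The case against.** **The windows are wide.** The delay allowed in section 6 fits inside the 12-week limit, and section 10 adds a scheduling allowance of one week either way. Few patients may be excluded. This stands as a limit on size. It does not remove the rule, because section 5.2 itself expects a significant proportion of patients to have chemotherapy between cycles.

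**The scenarios are assumed.** With 10% or 20% excluded the rates lie on both sides of 0.10, and the extreme cells need their own no-exclusion comparators. Both points stand: the figures show sensitivity, not an expected bias.

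**Section 5.5 does not clearly drop progressors.** A reader might infer from sections 5.5 and 5.7 that every patient removed for progression leaves the primary analysis, so that the endpoint event disqualifies the patient. The documents do not support this as the natural reading. Section 5.5 is about continuing with available vaccine, and its follow-up sentence concerns vaccination days. Sections 5.2, 5.9, 11.3 and 13.1.1 treat progression as the outcome to be followed and analysed. The likelier meaning is removed patients who take leftover vaccine. What stands is narrower: even then a progressor who takes that vaccine is dropped, and the literal wording reaches further than the context.

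**Progression before CKM.** Section 5.7 lets these patients continue, so an all-primed set must say how recurrence before priming is handled. This is right, and the fix covers it.

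**Conclusion.** The point holds for the booster-window rule. Section 5.2 makes membership of the primary set depend on post-baseline timing, section 13.3 leaves *evaluable* undefined, and nothing returns the excluded events to a single-arm test against fixed medians. This follows from the text and needs no simulation.

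Direction and size are unknown. If 10% are excluded, the null rejection rate runs from 0.06 to 0.31 as the relative hazard goes from 0.8 to 2.0. These figures rest on exponential TTP, the 15:40:60 mix, a null ratio of 1.0, and an assumed share and hazard that the documents do not give.

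Section 5.5 is a secondary ambiguity. On the literal reading, dropping progressions up to the one required scan gives 0.12 to 0.18 if all are dropped and 0.10 to 0.13 if a quarter or half are. A reader might take 0.42 as the plan's type I error. It is an upper bound on the target schedule that needs every progression in weeks 4–12 to be detected and dropped, and the required imaging does not provide that.

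The low cell number rule (section 8.1.2) and the priming-time limits are not part of the bias argument. The plan should be corrected; confidence is medium because the share affected is unknown.

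**What to change.** 1. In section 13.3, define *evaluable* and the primary efficacy set as all phase 2 patients who receive the priming dose and have no documented recurrence before it. List and report separately those with recurrence before priming.
2. State whether the two phase 1 patients who continue into phase 2 (section 5.1) belong to this set.
3. Count every later progression as an event, whatever the booster timing, completion or removal. Do not replace primed patients in this set.
4. Move the booster-window exclusion in section 5.2 to a secondary on-schedule sensitivity analysis, with a fixed landmark time after priming stated in advance. Booster 3 itself will not serve as the landmark, because it can fall anywhere from 12 to 36 weeks after priming.
5. Reword section 5.5 so that neither removal nor extra vaccine takes a patient out of the TTP analysis.

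**Cost.** Protocol wording only; section 5.9 already provides the follow-up. The downside is dilution by patients who do not complete the boosters. Simulated power at a true ratio of 1.25 with 168 patients is 0.88. It falls to 0.85, 0.83 or 0.76 if 5%, 10% or 20% of primed patients get no benefit. The sponsor should state the expected share and restate the power.

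**Separately.** Two schedule conflicts need to be reconciled: the 6 to 16 week priming window against the 3-month limit in the same section, and the booster 1 window (at least 4 weeks after priming) against the Week 4 table row (three weeks after Week 1), unless the one-week allowance in section 10 is meant to cover it.
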